7.4.2. Supplemental Albuterol/Salbutamol Use

Subjects should be instructed that study-provided albuterol/salbutamol should be used on an 'as-needed' basis only.

Rescue medication will be captured in the electronic Diary as well as eMDI as data allow. Details on how to place the eMDI on the MDI is described in the SPM.

Rescue inhaler use will be captured each day (during run-in, washout and treatment periods) by means of an eDiary and if available and possible in an eMDI device . The eDiary will be used as the primary analysis measure. eMDI attaches to the actual MDI inhaler and that gets activated every time there is an actuation. The device should be attached to the MDI inhaler at the first subject visit. If the subject requires a replacement rescue inhaler the eMDI device can be transferred from the old inhaler to the new on. This should be performed at the study site by the Investigator or designee.

Use of rescue albuterol/salbutamol should **not** be recorded as a concomitant medication in the eCRF.

The following Clinic visit Questionnaires will also be collected on the electronic diary:

7.4.3. COPD Assessment Test (CAT)

COPD-related health status will be assessed using the CAT at Visit 1 for subject characterisation and then Visits 2, 3, 4, 5, 6 and Visit 7.

The COPD Assessment Test (CAT) is a patient-completed instrument designed to provide a simple and reliable measure of health status in COPD. The CAT is designed to measure overall COPD-related health status for the assessment and long-term follow-up of individual patients. The instrument consists of eight items; each formatted as a semantic six-point differential scale, and is completed by the patient [Jones, 2009; Jones, 2012].

CAT will be completed at each visit on the eDiary. Additional instructions for completion of the CAT are provided in the SPM.

CAT evaluations must be performed before any other visit procedures.

7.4.4. Inhaler questionnaires

7.4.4.1. Inhaler Ease of Use

An investigator (or designee)-administered questionnaire will be completed at Visits 2 and 5, or Early Withdrawal if applicable, to determine the ease of use of the ELLIPTA and Respimat. Six questions will be asked and the subject will be required to select only one response for each question.

A sample of the inhaler ease of use questionnaire is included in the SPM. Additional instructions for completion of this questionnaire are provided in the SPM.

7.4.4.2. Inhaler Errors

Inhaler errors will be assessed using the Inhalers Errors Checklist at Visit 2 and Visit 5 to assess the critical and overall (critical and non-critical) errors made by subjects with the ELLIPTA and Respimat inhalers.

The investigator (or designee)-administered inhaler errors checklist is based on the steps listed in the Patient Information Leaflets (PIL) for each inhaler. The proportion of subjects reported by the investigator or designee as making at least one critical error (defined as an error that is most likely to result in no or only minimal medication being inhaled) or overall error (includes a critical and non-critical error) will be evaluated in this study.

The inhaler errors checklist will be administered by the investigator or designee.

At Visit 2 and 5, the subject will prepare his or her inhaler for first use and selfadminister their first dose of the study medication in the clinic under the supervision of the investigator or designee. The subject will simply follow the instructions in the patient information leaflet without prior instruction on the day. Any errors (critical or noncritical) made by the subject while using the inhaler will be recorded by the investigator or designee. If the subject makes no errors, this will also be recorded. Any errors (critical or non-critical) made by the subject while using the inhaler will be recorded by the investigator or designee. If the subject makes no errors, this will also be recorded. The investigator or designee will demonstrate the correct use of the inhaler to the subject and will make sure the inhaler is loaded properly before the subject leaves the clinic.

Additional instructions for completion of the inhaler errors checklist are provided in the SPM.

7.4.5. Any Medical Problems Experienced and any Medications used to Treat those Medical Problems

Signs and symptoms of COPD included on the electronic diary card will not be considered AEs and will not be collected in the eCRF.

7.5. Safety

Planned time points for all safety assessments are listed in the Time and Events Table (Section 7.1).

Safety endpoints include the following:

- Incidence of COPD exacerbations
- Incidence of adverse events

7.5.1. COPD Exacerbations

A moderate COPD exacerbation is defined as worsening symptoms of COPD that require treatment with oral/systemic corticosteroids and/or antibiotics. A severe exacerbation is defined as worsening symptoms of COPD that require in-patient hospitalization.

If a subject experiences a moderate or severe COPD exacerbation, the COPD exacerbation page of the eCRF should be completed. COPD exacerbations should not be recorded as an Adverse Event, unless they meet the definition of a Serious Adverse Event.

Subjects who experience a moderate or severe exacerbation during the run-in period will be withdrawn from the study and will not be allowed to be re-screened.

Signs and symptoms of COPD included on the electronic diary cards will not be considered AEs and will not be recorded in the eCRF.

The time period for collection of COPD exacerbations will be from the Pre-Screening (Visit 0) until completion of the follow-up contact. If a subject experiences a COPD exacerbation from the time the ICF is signed until randomization, summary information (yes/no status question) will be collected. COPD exacerbations after randomization through follow-up will be recorded on the COPD exacerbation page of the eCRF.

7.5.2. Adverse Events (AE), Serious Adverse Events (SAEs) and sentinel events

The definitions of an AE or SAE and sentinel event can be found in Section 12.4.

The investigator and their designees are responsible for detecting, documenting and reporting events that meet the definition of an AE or SAE.

7.5.2.1. Time period and Frequency for collecting AE and SAE information

- AEs will be collected from the start of study treatment and until the follow up contact.
- AEs and SAEs will be collected at the time points specified in the Time and Events Table (Section 7.1).

- Medical occurrences that begin prior to the start of study treatment but after obtaining informed consent may be recorded on the Medical History/Current Medical Conditions section of the CRF.
- Any SAEs assessed as related to study participation (e.g., protocol-mandated procedures, invasive tests, or change in existing therapy) or related to a GSK product will be recorded from the time a subject consents to participate in the study up to and including any follow-up contact.
- All SAEs will be recorded and reported to GSK within 24 hours, as indicated in.
- Investigators are not obligated to actively seek AEs or SAEs in former study subjects. However, if the investigator learns of any SAE, including a death, at any time after a subject has been discharged from the study, and he/she considers the event reasonably related to the study treatment or study participation, the investigator must promptly notify GSK.

NOTE: The method of recording, evaluating and assessing causality of AEs and SAEs plus procedures for completing and transmitting SAE reports to GSK are provided in Section 7.5.2.1

7.5.2.2. Method of Detecting AEs and SAEs

Care will be taken not to introduce bias when detecting AEs and/or SAEs. Open-ended and non-leading verbal questioning of the subject is the preferred method to inquire about AE occurrence. Appropriate questions include:

- "How are you feeling?"
- "Have you had any (other) medical problems since your last visit/contact?"
- "Have you taken any new medicines, other than those provided in this study, since your last visit/contact?"

7.5.2.3. Follow-up of AEs and SAEs

After the initial AE/SAE report, the investigator is required to proactively follow each subject at subsequent visits/contacts. All SAEs and non-serious AEs of special interest (as defined in Section 7.5.2) will be followed until resolution, until the condition stabilizes, until the event is otherwise explained, or until the subject is lost to follow-up (as defined in Section 5.5).

7.5.2.4. Cardiovascular Events

Investigators will be required to fill out event specific data collection tools for the following AEs and SAEs:

- Myocardial infarction/unstable angina
- Congestive heart failure
- Arrhythmias
- Valvulopathy

- Pulmonary hypertension
- Cerebrovascular events/stroke and transient ischemic attack
- Peripheral arterial thromboembolism
- Deep venous thrombosis/pulmonary embolism
- Revascularisation

This information should be recorded in the specific cardiovascular eCRF within one week of when the AE/SAE(s) are first reported.

7.5.2.5. Pneumonia Events

Investigators will be required to fill out a pneumonia event specific eCRF within one week of when the pneumonia AE/SAE(s) is first reported.

7.5.2.6. Death Events

In addition, all deaths will require a specific death data collection tool to be completed. The death data collection tool includes questions regarding cardiovascular (including sudden cardiac death) and non-cardiovascular death.

This information should be recorded in the specific death eCRF within one week of when the death is first reported.

7.5.2.7. Disease-Related Events and/or Disease-Related Outcomes Not Qualifying as SAEs

The following disease related events (DREs) are common in subjects with COPD and can be serious/life threatening:

• COPD exacerbation

COPD exacerbations are associated with the disease to be studied and will not be recorded as AEs unless the exacerbation meets the definition of a 'serious' AE. Exacerbations that meet the definition of 'serious' AEs will be recorded on the appropriate eCRF section and should be reported to GSK for all subjects regardless of whether or not they are randomized to study medication. Signs and symptoms of COPD included on the electronic diary will not be considered AEs and will not be recorded in the eCRF.

7.5.2.8. Regulatory Reporting Requirements for SAEs

Prompt notification by the investigator to GSK or designee of SAEs and non-serious AEs related to study treatment (even for non- interventional post-marketing studies) is essential so that legal obligations and ethical responsibilities towards the safety of subjects and the safety of a product under clinical investigation are met.

GSK has a legal responsibility to notify both the local regulatory authority and other regulatory agencies about the safety of a product under clinical investigation. GSK will comply with country specific regulatory requirements relating to safety reporting to the

CONFIDENTIAL

regulatory authority, Institutional Review Board (IRB)/Independent Ethics Committee (IEC) and investigators.

Investigator safety reports are prepared for suspected unexpected serious adverse reactions according to local regulatory requirements and GSK policy and are forwarded to investigators as necessary.

An investigator who receives an investigator safety report describing a SAE(s) or other specific safety information (e.g., summary or listing of SAEs) from GSK will file it with the IB and will notify the IRB/IEC, if appropriate according to local requirements.

7.5.3. Pregnancy

- Any pregnancy that occurs during study participation must be reported using a clinical trial pregnancy form. To ensure subject safety, each pregnancy must be reported to GSK within 2 weeks of learning of its occurrence. The pregnancy must be followed up to determine outcome (including premature termination) and status of mother and child. Pregnancy complications and elective terminations for medical reasons must be reported as an AE or SAE. Spontaneous abortions must be reported as an SAE.
- Any SAE occurring in association with a pregnancy, brought to the investigator's attention after the subject has completed the study and considered by the investigator as possibly related to the study treatment, must be promptly reported to GSK.
- If a pregnancy is reported then the investigator should inform GSK within 2 weeks of learning of the pregnancy and should follow the procedures outlined in Appendix 6.

7.5.4. Liver Chemistry Stopping Criteria

A protocol-defined liver chemistry stopping criteria and increased monitoring algorithm is provided in Figure 2.

Figure 2 Phase III/Phase IV Liver Stopping and Increased Monitoring Algorithm

Liver Safety Required Actions and Follow up Assessments Section can be found in Appendix 2

Phase III-IV Liver Chemistry Increased Monitoring Algorithm with Continued Therapy for ALT ≥3xULN but <8xULN

Liver Safety Required Actions and Follow up Assessments Section can be found in Appendix 2

Note: This study does not require laboratory assessments, therefore the liver chemistry criteria apply to any laboratory assessments obtained outside of the protocol-specified safety evaluations.

7.5.5. Medical Device Incidents (Including Malfunctions)

Procedures for Documenting Medical Device Incidents are provided in Appendix 5

7.5.6. Physical Exams

A complete physical examination will be performed at Visit 1 screening and at Visit 7 or Early Withdrawal Visit if appropriate.

Planned time points for all safety assessments are listed in the Time and Events Table (Section 7.1).

8. DATA MANAGEMENT

- For this study subject data will be entered into GSK defined electronic case report forms (eCRFs), transmitted electronically to GSK or designee and combined with data provided from other sources in a validated data system.
- Management of clinical data will be performed in accordance with applicable GSK standards and data cleaning procedures to ensure the integrity of the data, e.g., removing errors and inconsistencies in the data.
- Adverse events and concomitant medications terms will be coded using MedDRA (Medical Dictionary for Regulatory Activities) and an internal validated medication dictionary, GSKDrug.
- CRFs (including queries and audit trails) will be retained by GSK, and copies will be sent to the investigator to maintain as the investigator copy. Subject initials will not be collected or transmitted to GSK according to GSK policy.

9. STATISTICAL CONSIDERATIONS AND DATA ANALYSES

9.1. Hypotheses

The primary objective of this study is to compare UMEC/VI 62.5/25 mcg with TIO/OLO 5/5 mcg in moderate COPD subjects. The primary endpoint is trough FEV₁ at Week 8. The primary analysis is the comparison of this endpoint for UMEC/VI 62.5/25 mcg vs. TIO/OLO 5/5 mcg.

The null hypothesis is that the difference in trough FEV_1 between treatment groups is less than or equal to a pre-specified non-inferiority margin Δ :

 $H_0: T_1 - T_2 \leq \Delta$

The alternative hypothesis is that the difference between treatment groups is greater than the margin.

 $H_1:\,T_1-T_2\geq\Delta$

where T_1 and T_2 are the treatment means for UMEC/VI 62.5/25 mcg and TIO/OLO 5/5 mcg, respectively.

The non-inferiority margin has been set at -50mL, which is consistent with the noninferiority margins used for trough FEV₁ or 0 to 24 hour weighted mean FEV₁ in previous studies comparing long-acting bronchodilators or long-acting bronchodilator/ICS combinations [Ichinose, 2010; Vogelmeier, 2010; Agustí, 2014].

If the lower bound of the 95% confidence interval around the (UMEC/VI 62.5/25 mcg vs. TIO/OLO 5/5 mcg) treatment difference is above -50mL then UMEC/VI 62.5/25 mcg will be considered non-inferior to TIO/OLO 5/5 mcg.

If the lower bound of the 95% confidence interval around the (UMEC/VI 62.5/25 mcg vs. TIO/OLO 5/5 mcg) treatment difference is above 0 then UMEC/VI 62.5/25 mcg will be considered superior to TIO/OLO 5/5 mcg.

9.2. Sample Size Considerations

9.2.1. Sample Size Assumptions

The sample size calculations use a one-sided 2.5% significance level and an estimate of within-subject standard deviation (SD) for trough FEV_1 of 140 ml. The estimate of SD is based on a mixed model repeated measures (MMRM) analyses of two previous cross-over studies in COPD subjects evaluating trough FEV_1 at Week 2. The observed SD from these studies (133ml in DB2116132 and 113ml in DB2116133) has been increased to allow for additional variability that may be observed during an 8 week treatment period.

A study with 168 evaluable subjects for the primary analysis on the per-protocol (PP) population will have 90% power to detect non-inferiority of UMEC/VI to TIO/OLO based on trough FEV_1 at Week 8, when the margin of non-inferiority is -50mL and the true mean treatment difference is assumed to be 0mL.

It is estimated that approximately 10% of subjects who will provide a Week 8 assessment will be excluded from the PP population, which would require 186 subjects with a Week 8 assessment in the ITT population. Allowing for a 15% withdrawal rate, a total of 220 subjects will be randomised.

9.2.2. Sample Size Sensitivity

The within-subject SD of 140 ml for trough FEV₁ used for the sample size calculations was based on two previous cross-over responder studies in COPD subjects evaluating trough FEV₁ at Week 2. If the standard deviation observed in this study is different from the estimated value used in the sample size calculation, the power to determine non-inferiority based on trough FEV₁ at Week 8 will be affected. Table 4 illustrates the power which would be obtained with various standard deviations, assuming the number of evaluable subjects remains constant at 168 and the non-inferiority margin is -50 mL.

Within-subject SD (mL)	Power for Margin of -50 mL
100	>99%
120	97%
140	90%
160	81%
180	72%

Table 4Impact on Power of Different Estimates of Standard Deviation for
Trough FEV1

If the within subject SD increased to 180 mL, the study would have 72% power to conclude non-inferiority based on a margin of -50 mL. If the SD were 100 mL then the study would have >99% power to conclude non-inferiority.

Based on a within subject SD of 140 mL and a sample size of 168 evaluable PP subjects, the lower confidence bound for the treatment difference would be greater than 0 at an observed treatment difference of 30 mL [detectable effect].

Based on a within subject SD of 140 mL and a sample size of 186 ITT subjects, the study would conclude superiority (i.e. lower confidence bound > 0) with a treatment difference of 29mL [detectable effect].

9.2.3. Sample Size Re-estimation or Adjustment

No sample size re-estimation is planned for this study.

9.3. Data Analysis Considerations

9.3.1. Analysis Populations

Three subject populations will be identified.

The **All Subjects Enrolled** Population will comprise all subjects for whom a record exists on the study database, including screen failures and any subject who was not screened but experienced a serious adverse event (SAE) between the date of informed consent and the planned date of the Screening Visit. This population will be used for reporting subject disposition, reasons for withdrawal prior to randomization, and inclusion, exclusion and randomization criteria deviations and SAEs for non-randomised subjects.

The **Intent-to-treat** (ITT) Population will comprise all subjects randomized to treatment, excluding those who were randomized in error. A subject who is recorded as a screen or run-in failure and also randomized will be considered to be randomized in error. Any other subject who receives a randomization number will be considered to have been randomized. Randomized subjects will be assumed to have received study medication unless definitive evidence to the contrary exists. Outcomes will be reported according to the randomized treatment allocation. This population will be the used for all efficacy and safety displays unless specified otherwise.

The **Per Protocol** (PP) Population will comprise all subjects in the ITT Population who do not have a full protocol deviation considered to impact efficacy. Receipt of a study treatment other than the randomised treatment will be considered a full protocol deviation. Subjects with partial protocol deviations considered to impact efficacy will be included in the PP Population but will have their data excluded from PP analyses from the time of deviation onwards. Subjects with time-point specific or period specific protocol deviations will be included in the PP population but will have the data affected excluded from PP analyses. The definition of full, partial, time-point specific and period specific deviations considered to impact efficacy will be included in the Reporting and Analysis Plan (RAP). This population will be used for the primary comparison between the treatments to determine NI. It will also be used for the primary comparison between treatments to assess superiority, assuming that the primary analysis on the PP population supports the conclusion of NI.

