The PP population will be used for the treatment comparison of the primary endpoint of trough FEV_1 at Week 8 for non-inferiority and superiority.

The margin of non-inferiority is -50mL and the true mean treatment difference is assumed to be 0mL. The non-inferiority margin of -50mL has been chosen which is consistent with the non-inferiority margins used for trough FEV_1 or 0 to 24 hour weighted mean FEV_1 in previous studies comparing long-acting bronchodilators or longacting bronchodilator/ICS combinations [Ichinose, 2010; Agustí, 2014]. Therefore, if the lower confidence interval (2.5% one-sided significance level) of the statistical testing should fall above -50mL then UMEC/VI may be deemed to be statistically non-inferior to OLO/TIO.

If non-inferiority is observed, the testing procedure will continue to examine statistical superiority. Superiority of UMEC/VI over OLO/TIO would be claimed provided the lower bound of the 95% confidence interval is above 0 for the treatment difference and a treatment difference of approximately 50mL is obtained.

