9.4. Key Elements of Analysis Plan

Since this is an 8 week non-inferiority study with two active comparators, the number of withdrawals is expected to be low. In particular, subjects who experience an exacerbation whilst in the study will be allowed to continue participating if possible. Furthermore, the primary comparison is non-inferiority on the per protocol population (a De Jure estimand) and inclusion of data from subjects post-withdrawal would likely bias the results towards a conclusion of non-inferiority. Hence data from subjects post-withdrawal will not be collected. Where possible, data from subjects who withdraw prematurely from the study will be included in any relevant analyses. Specific details for inclusion will be detailed in the RAP, but in general the minimum data required will be a baseline evaluation and at least one on-treatment evaluation. Tipping Point analyses will however be conducted to assess robustness of conclusions. Data collected during a clinic visit will be reported by the visit at which the data were collected and will not be excluded from any analysis for being collected outside of an assessment window.

For the purposes of analyses, a completed subject is defined as anyone completing the last treatment visit for each period (Visit 4 and 7).

It is anticipated that approximately 30 centres (worldwide) will participate in the study. Centres enrolling a small number of subjects may be pooled with another centre. All amalgamations will be finalised and documented in the RAP. These amalgamations will be used wherever region is incorporated into the analysis.

Baseline values for each endpoint will be those used from Visit 1 (screening) or pretreatment in period 1 at Visit 2 (randomisation) or pre-treatment in period 2 at Visit 5 and will be defined in the RAP.

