9.4.1. Efficacy Analyses

All efficacy data will be summarized using means, SDs and ranges for continuous data and frequencies and percentages for categorical data.

Primary Endpoint

The primary endpoint of trough FEV_1 at week 8 will be analysed using a repeated measures model including data recorded at each of Week 4 and Week 8 for the PP population. Treatment group (categorical) will be fitted as the explanatory variable, with period baseline, mean baseline, period, and visit fitted as covariates. Visit (nominal) will be fitted as a categorical variable and visit by period baseline, visit by mean baseline and visit by treatment interaction terms will be included. Treatment effects will be estimated at each visit separately. The variance-covariance matrix will be assumed unstructured. Missing data are not imputed in this analysis; however, all non-missing data will be used within the analysis to estimate the treatment effect at Week 8.

Estimated treatment differences for UMEC/VI vs. TIO/OLO will be presented together with 95% confidence intervals (CIs) for the difference and p-values (for test of superiority).

The MMRM analysis of the primary endpoint will be repeated for the ITT Population testing for superiority in order to ensure consistent results with those from the PP population. These analyses will include data from protocol deviators. In addition, a tipping point analysis will be carried out as a sensitivity analysis for the primary endpoint of trough FEV_1 at Week 8 on the PP and ITT population in order to assess the impact of missing data. Full details will be given in the RAP.

Other Endpoints

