2. SUMMARY OF KEY PROTOCOL INFORMATION

2.1. Changes to the Protocol Defined Statistical Analysis Plan

Any changes from the originally planned statistical analysis specified in the protocol GlaxoSmithKline Document Number 2015N256437_00 are outlined in Table 1.

Protocol		Re	porting & Analysis Plan		
Statistic	al Analysis Plan	Sta	tistical Analysis Plan	Ra	tionale for Changes
• Time deteri	to clinically important ioration composite endpoint	•	Time to clinically important deterioration composite endpoint will not be analysed	•	Study deemed too short to assess and SGRQ is not collected.
 Propo accor ≥1 ur from 	ortion of responders ding to CAT (defined as a hit improvement in score baseline) at Weeks 4 and 8	•	Proportion of responders according to CAT (defined as a ≥ 2 unit improvement in score from baseline) at Weeks 4 and 8	•	Typographical error
 ITT p All rai exclu rando who i run-ir rando be rai other rando consi rando Displa treatr was r 	opulation definition ndomized subjects, ding those who were omized in error. A subject s recorded as a screen or a failure and also omized will be considered to ndomized in error. Any subject who receives a omization number will be dered to have been omized. ays will be based on the nent to which the subject andomized.	•	ITT population definition now includes – received at least one dose of study medication. All randomized subjects, excluding those who were randomized in error and received at least one dose of study medication. A subject who is recorded as a screen or run-in failure and also randomized will be considered to be randomized in error. Any other subject who receives a randomizet on have been randomized. Displays will be based on the treatment to which the subject was randomized.	•	For consistency with prior GSK573719 + GW642444 studies
• No In	haler Naive population	•	Inhaler Naive population definition All subjects in the ITT population who have not used either Ellipta or Respimat for 6 months prior to inhaler evaluation (Visit 2	•	Population for Inhaler summaries and analysis

Table 1 Changes to Protocol Defined Analysis Plan

Protocol	Reporting & Analysis Plan	
Statistical Analysis Plan	Statistical Analysis Plan	Rationale for Changes
	 or Visit 5). This population will be used for all Inhaler assessment displays unless stated otherwise. 	

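### The superiority criterion is stated in two conflicting versions, one with an undefined extra condition of about 50 mL; separately, superiority is decided on the Per Protocol population with no stated reason

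*Protocol*

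**What the plan says.** **Criterion.** Protocol 4.4 lets the testing continue to superiority once non-inferiority is seen. It then sets two conditions: a lower 95% bound above 0, and that "a treatment difference of approximately 50mL is obtained". Elsewhere there is one condition. Protocol 9.1 says that if the lower bound for the "treatment difference is above 0 then UMEC/VI 62.5/25 mcg will be considered superior to TIO/OLO 5/5 mcg". The synopsis and SAP 1 and 2.4 say the same. Protocol 9.2.2 states that, with 186 ITT subjects, "the study would conclude superiority (i.e. lower confidence bound > 0) with a treatment difference of 29mL". The tipping-point rule in SAP 7.1.2 also judges superiority by the lower limit alone.

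**Population.** Protocol 4.4 says "The PP population will be used for the treatment comparison of the primary endpoint" for both non-inferiority and superiority. Protocol 9.3.1 says of PP that "It will also be used for the primary comparison between treatments to assess superiority", provided non-inferiority holds in PP, and SAP 1 repeats this. The ITT analysis of the primary endpoint "will be repeated for the ITT Population testing for superiority in order to ensure consistent results" with PP (Protocol 9.4.1). If the two are inconsistent, SAP 7.1.1 provides for further investigation and gives no decision rule. Treatment is open label (Protocol 6.4).

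**The concern.** A superiority rule has to give one answer for any observed result. Here, a PP difference of 40 mL with a lower limit above 0 is superior under Protocol 9.1 and arguably not superior under Protocol 4.4. Because "approximately" carries no number, 4.4 cannot be applied as a rule at all.

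More depends on this than a label. Under SAP 2.4, non-lung-function endpoints open for inference at non-inferiority, but the lung-function ones open only if superiority is established on the primary endpoint.

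The population question is secondary. Superiority can be claimed on PP while the ITT lower limit is not above 0. The lung-function endpoints that this claim opens are mainly analysed on ITT: FVC, IC and FEV1 responders are analysed on ITT only (SAP 8.1.1 and 10.13.5). The gate and most of what lies behind it therefore use different populations.

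**Working it through.** **Inputs.** Within-subject SD 140 mL, PP n = 168, margin −50 mL, one-sided 2.5% (Protocol 9.2.1); SDs of 100 to 180 mL (Protocol Table 4); ITT n = 186 (Protocol 9.2.2). For the two-period crossover, SE = SD × √(2/n). The lower limit clears 0 when the observed difference exceeds t(0.975, n−2) × SE.

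**Reproducing the plan.** PP: SE = 140 × √(2/168) = 15.28 mL. Non-inferiority power at a true 0 mL (noncentral t, noncentrality 50/15.28) is 90.2%; the plan states 90%. Over Table 4's SDs the same formula gives 99.5, 96.7, 90.2, 81.3 and 71.6%, matching the table. The lower limit clears 0 at 1.974 × 15.28 = 30.2 mL (plan: 30). ITT: SE = 140 × √(2/186) = 14.52 mL and 1.973 × 14.52 = 28.6 mL (plan: 29). No stated number is wrong.

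**Does the extra condition bind?** On PP, the lower limit clears 0 at 21.5, 25.9, 30.2, 34.5 and 38.8 mL for SDs of 100, 120, 140, 160 and 180. All are below 50 mL, so a 50 mL floor decides the claim at every SD in Table 4.

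**How often do the versions disagree?** Version A is lower limit above 0. Version B adds an observed difference of at least a floor, which the documents leave undefined; 40 to 55 mL is assumed here. P(A) comes from the noncentral t. Since these floors lie well above 30.2 mL, P(B) is close to 1 − Φ((floor − true)/15.28). For example, at floor 50 and true 40 it is 1 − Φ(0.655) = 25.6%. Disagreement is P(A) − P(B).

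| True difference (mL) | P(A) | P(B), floor 40 | P(B), floor 50 | P(B), floor 55 | Disagreement, floor 40 to 55 |
|---|---|---|---|---|---|
| 20 | 25.5% | 9.5% | 2.5% | 1.1% | 16–24% |
| 30 | 49.7% | 25.6% | 9.5% | 5.1% | 24–45% |
| 40 | 74.0% | 50.0% | 25.6% | 16.3% | 24–58% |
| 50 | 90.2% | 74.4% | 50.0% | 37.2% | 16–53% |

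At a true 0 mL, A claims superiority in 2.5% of trials and B (floor 50) in 0.05%. Neither version inflates the error rate; they are simply different rules.

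**Population.** Suppose exclusions are unrelated to outcome and the 168 are nested in the 186, so the two estimates correlate at √(168/186) = 0.950. Superiority on PP only then occurs in 0.7, 3.1 and 3.2% of trials at true differences of 0, 20 and 30 mL, and on ITT only in 0.7, 5.4 and 7.4%. These are disagreement rates, not error rates. The model drops whole subjects; partial deviators keep some data in PP (Protocol 9.3.1), so real disagreement may be smaller.

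**The case against.** **The 50 mL phrase is a stray remark.** It appears once, in a design-justification section. The hypotheses, the detectable effects and every SAP decision rule use the lower limit alone, so an analyst following the SAP has one rule. This largely stands, and it is why deleting the phrase is the natural repair. But 4.4 words it as a condition for a claim, and nothing in either document withdraws it.

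**SAP Table 1.** That section sets out "Any changes from the originally planned statistical analysis specified in the protocol" and does not mention 50 mL. A reader might infer that the condition is therefore still formally in force. The documents do not support that: Protocol Section 9, which holds the planned analysis, never contained the condition, so there was nothing there for Table 1 to drop.

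**A single disagreement figure.** Reading the floor as exactly 50 mL gives 23, 40, 48 and 40% at true differences of 20, 30, 40 and 50 mL. That is more precise than "approximately" permits; the ranges above are what can be defended.

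**PP for superiority is a consistent, prespecified choice.** That stands. A reader might infer that it biases the claim or inflates its error. The documents do not show this. PP holds 2.5% if exclusions are unrelated to outcome, spirometry testers are blinded (Protocol 4.4), exclusions are agreed before code release (SAP 3.1), and tipping-point analyses cover both populations (SAP 7.1.1). The full deviation list sits in a separate plan (SAP 10.1.1), so how far open-label knowledge could affect exclusions cannot be judged here.

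Nor does Protocol 9.4 offer a rationale for PP limited to non-inferiority. Its statement that "the primary comparison is non-inferiority on the per protocol population (a De Jure estimand") strictly supports not collecting post-withdrawal data. What remains is that no reason is given for PP in the superiority test.

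**Conclusion.** The conflict in the superiority criterion is wrong as written and should be fixed before the randomisation codes are released. At SD 140 mL and PP n = 168, an observed difference of about 30 to 50 mL changes status with the section consulted. At a true 50 mL, superiority power is 90% without a floor and 37 to 74% with one. These figures rest on the plan's SD, complete pairs, and an assumed floor of 40 to 55 mL.

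The population point is a low-cost improvement, not an error. It rests on four facts: no reason is stated for PP, Protocol 9.2.2 ties its superiority conclusion to the ITT subjects, the ITT test is already planned, and disagreement between populations has no decision rule. No bias, direction of bias or error inflation is claimed.

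**What to change.** **Criterion.** State one rule in every place. Either delete the 50 mL phrase from Protocol 4.4, or label it a benchmark of relevance and not a condition, as the other sections imply. Otherwise give one exact threshold in Protocol 1, 4.4, 9.1 and 9.2.2 and SAP 1, 2.4 and 7.1.2. Deletion costs only wording. Keeping a threshold costs the power shown above.

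**Population.** In Protocol 4.4, 9.3.1 and 9.4.1 and SAP 1, 2.4, 4 and 7.1.1, keep PP primary for non-inferiority. Once that is shown, base superiority on the lower limit of the planned ITT repeated-measures analysis being above 0, and open the lung-function endpoints on the same result. Report PP alongside as supportive.

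No extra subjects or analyses are needed. At SD 140 mL, ITT power is 54% against 50% on PP at a true 30 mL, and 93% against 90% at 50 mL. The drawback is that ITT includes deviators' data, so its SD may be higher. The advantage is gone at an ITT SD of 30.16 / (1.973 × √(2/186)) = 147 mL. At SD 160 the lower limit clears 0 only at 32.7 mL, and power is 44% at 30 mL and 85% at 50 mL. ITT would also allow a claim that PP does not support, and it does not restore post-withdrawal data, which are not collected (Protocol 9.4). If the sponsor prefers PP, a stated reason and a rule for PP/ITT disagreement would be the minimum.
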